# 1. Aims

- 1.1. The goal of this single arm Phase II study is to evaluate the prophylactic use of Trental and vitamin E for its efficacy in reducing radiation necrosis after radiosurgery.
- 2. Background and Significance
  - 2.1. Hypothesis:
    - 2.1.1. Vitamin E and Trental are commonly used in combination to treat cerebral radiation necrosis after radiosurgery. Use of these drugs after radiosurgery may serve as prophylaxis for and reduce the incidence of radiation necrosis.
  - 2.2. Background:
    - 2.2.1. Radiation Necrosis Review:
      - Radiosurgery is widely used in the treatment of various intracranial 2.2.1.1. disorders such as metastatic brain tumors, meningiomas and arteriovenous malformations (1-3). However, the use of radiosurgery is limited by the risk of injury to adjacent brain. Although technological advances have considerably enhanced the safety and efficacy of radiosurgery, radiation necrosis continues to be a serious complication of treatment. A recent study at our institution showed that 14% of metastatic lesions treated with radiosurgery exhibited imaging characteristics consistent with radiation necrosis (4). Several other studies have confirmed this observation and have shown that radiographic changes can be present in up to 46% (5-7). Typically, radiation injury is categorized into acute, subacute and chronic stages based upon the time between radiation treatment and onset of symptoms (8). Imaging characteristics are variable and can range from T2 FLAIR abnormalities to areas of contrast enhancement and frank necrosis. Clinical symptoms can be associated with these radiographic changes and can range from mild headaches to progressive neurologic deterioration. Steroids are a commonly used form of treatment for radiation induced injury. However, patients who progress despite steroid treatment are often candidates for oral therapy with Trental and vitamin E. This combination has been widely used to treat radiation induced injury and will often reverse both clinical and radiographic effects (9-16). A recent randomized controlled trial showed that this combination is effective in the treatment of superficial radiation induced fibrosis over the chest, in patients receiving radiotherapy for breast cancer (13). Also, a recent study suggested that the combination may be effective in the treatment of radiation induced brain injury (14). The goal of this study is to determine whether this commonly used treatment for radiation necrosis can be used prophylactically to prevent, delay and/or reduce the severity of cerebral radiation necrosis after radiosurgery.

- 3. Investigator Experience
  - 3.1. [name] is a board-certified neurosurgeon who has undergone fellowship training in neurosurgical-oncology at the University of San Francisco. He has published extensively in the field of neurosurgical oncology and currently has an academic neurosurgical practice with an active oncology component. He has also had extensive experience in the diagnosis and treatment of central nervous system radiation necrosis.
  - 3.2. [name] is a board-certified radiation oncologist. He has published extensively in the field of radiation oncology and currently has an academic radiation oncology practice. He has also had extensive experience in the diagnosis and treatment of central nervous system radiation necrosis.
- 4. Experimental Design and Methods
  - 4.1. Patient Registration:
    - 4.1.1. Only patients who meet eligibility requirements may be registered.
    - 4.1.2. Once an eligible patient is identified by the treating physician, informed consent for participation in the study is obtained.
    - 4.1.3. A baseline evaluation form and enrollment form (See Appendix B) is completed.
  - 4.2. Pretreatment Evaluation:
    - 4.2.1. Prior to initiation of treatment, a complete history and physical with a detailed neurologic examination is required.
    - 4.2.2. Evaluation of further metastatic disease may be performed as clinically indicated.
  - 4.3. Treatment Phase:
    - 4.3.1. Patients will receive a combination of Trental 400 mg TID and Vitamin E 400IU BID starting the first day after the last radiosurgery treatment. This regimen is then continued on a daily basis for a period of 6 months after the last radiosurgery treatment.
    - 4.3.2. Patients will be monitored with regular clinic visits and MRIs performed at 3 month intervals. A follow up form (Appendix B) will be filled out by the treating physician at each visit.
    - 4.3.3. All patients will be followed for an appropriate duration as clinically indicated.
    - 4.3.4. Enrolled patients that require additional radiosurgery will discontinue Trental and Vitamin E for the two weeks prior to the additional radiosurgery and resume treatment the day after. These patients will remain on study, but the new site disease will not be followed in the necrosis analysis.
  - 4.4. Data Analysis and Monitoring
    - 4.4.1. Study Endpoints:
      - 4.4.1.1. Primary
        - 4.4.1.1.1. Incidence of symptomatic radiation necrosis
        - 4.4.1.1.2. Incidence of asymptomatic radiation necrosis
      - 4.4.1.2. Secondary
        - 4.4.1.2.1. Change in volume of contrast enhancement
        - 4.4.1.2.2. Change in volume of necrosis

- 4.4.1.2.3. Change in volume of T2 edema
- 4.4.1.2.4. Steroid usage
- 4.4.2. Results of the Data analyses will be reported over all as well as by stratifying with respect to:
  - 4.4.2.1. Radiation prescription dose
  - 4.4.2.2. Lesion volume
  - 4.4.2.3. Presence of comorbidities: Hypertension, Diabetes
- 4.4.3. As per the design, at the first stage we would evaluate the results by identifying when we have 8 lesions with necrosis. If at that stage, we have 52 or more lesions in the study then that would confirm we should continue to complete the study with all 134 lesions. At that stage, if we find 14 or less lesions with radiation necrosis, we would then claim that the study has met its objective of a 50% reduction in incidence of radiation necrosis (from 15% to 7.5%). (see Appendix A)
- 4.4.4. Summary of Data Submission (See Appendix B)

Follow MRI Form (MF)

- 4.4.4.1. Enrollment Form (EF)
- 4.4.4.2. Initial Evaluation Form (IF)
- 4.4.4.3. Treatment Form (TF)
- 4.4.4.4. Follow Up Form (FF)
- Within 2 wks of registration Within 2 wks of registration At the end of radiosurgery
- Every 3 months for 1 year
- Every 3 months for 1 year
- 4.4.5. Treatment Form (TF) will be completed by treating physician.
- 4.4.6. MRI documentation

4.4.4.5.

- 4.4.6.1. The contrast-enhanced MRI performed pre-radiosurgery and every 3 months post-radiosurgery will be evaluated by the investigators: REW, JB, LI. Form MF will be completed by investigator LI.
- 4.4.6.2. Radiation necrosis will be defined as previously reported by Blonigen et al. (4):

A combination of criteria will be used including appearance on serial MRI scans, MR Spectroscopy and histology (when available). It will be further described as the following: (1) patient with radiographic changes with a requirement of steroid therapy, (2) 2 consecutive scans with persistent MRI changes consistent with radiation necrosis, (3) findings suggestive of radiation necrosis on MR Spectroscopy, or (4) histological evidence of radiation necrosis.

- 4.4.6.3. Once radiation necrosis is identified by the treating physician, parameters will be quantified using standard radiation oncology software tools by an investigator: LI. The volume of contrast enhancement, T2 edema and necrosis will be quantified.
- 4.5. Data storage and confidentiality
  - 4.5.1. Data will be maintained in a password protected database and will only be accessed by the listed investigators. The information gathered will not be used or disclosed for any other purpose other than this specific research project.

- 5. Estimated period of time to complete the study.
  - 5.1. It is estimated that the patient recruitment period will be 2 years and the follow up period will be one year. Total estimated time to complete the study is 3 years.
- 6. Human Subjects: Describe the characteristics of the research population:
  - 6.1. Subjects will include patients receiving or planning to undergo single fraction or five fraction radiosurgery for a metastatic brain tumor.
  - 6.2. The demographics of the study population are expected to reflect the general population with intracranial metastatic tumors. Only adults  $\geq$  18 years of age will be included in the study.
  - 6.3. Recruitment:
    - 6.3.1. Patients seen at the University of Cincinnati Brain Tumor Center will be directly recruited by the treating physician.
  - 6.4. This study is estimated to require 49 patients. In a recently published study performed at the University of Cincinnati (4), patients recruited to the study had an average of 2.75 metastatic lesions. Each lesion was treated independently when analyzing the incidence of radiation necrosis. Using this same method, a total of 134 lesions are necessary to show a 50% effective reduction in radiation necrosis with our supplement. This would be estimated to require 49 patients.
  - 6.5. Inclusion Criteria:
    - 6.5.1. Patients about to undergo or currently receiving single or five fraction radiosurgery for a metastatic brain tumor.
    - 6.5.2. Diagnosis of a metastatic brain tumor may be accomplished by histologic confirmation or by clinical confirmation by the treating physician based on MR Imaging characteristics in the setting of a known history of cancer.
    - 6.5.3. Availability for follow up
    - 6.5.4. Ability to give informed consent.
    - 6.5.5. Age  $\geq$  18 years
    - 6.5.6. Patients who have had partial or total resection of a metastatic tumor are eligible.
  - 6.6. Exclusion Criteria:
    - 6.6.1. Known sensitivity to vitamin E or Trental
    - 6.6.2. Pregnant or nursing women.
    - 6.6.3. Recent intracranial bleed or retinal hemorrhage
    - 6.6.4. Major medical or psychiatric illness which in the investigators opinion will prevent administration or completion of the protocol therapy and/or interfere with followup.
    - 6.6.5. Treatment with a non-approved or investigational drug within 30 days before day 1 of study treatment.
    - 6.6.6. History of Avastin treatment.
    - 6.6.7. Anticipated need for treatment with Avastin.
    - 6.6.8. Patients currently on vitamin E or Trental are ineligible.
    - 6.6.9. History of bleeding disorder
    - 6.6.10. Patient who is on Warfarin, Lovenox, NSAIDS, or aspirin. Low dose (81 mg) of daily aspirin is acceptable.

- 6.6.11. History of liver disorder
- 6.6.12. Intolerance to methylxanthines such as caffeine, theophylline, and theobromine.
- 7. Risk/Benefit Assessment.
  - 7.1. The combination of vitamin E and Trental is a commonly used treatment for radiation induced injury to the brain as well as other body organs (9-14).
  - 7.2. Vitamin E ( $\alpha$ -tocopherol):
    - 7.2.1. It is thought that the therapeutic benefits in combating radiation induced injury are due to its antioxidant properties and its inhibition of TGF- $\beta$  and collagen production (15,16). As a common component in over the counter multivitamins, the toxicity profile of vitamin E is low and the dosage of 400 IU BID used for the study presents minimal risk to the patient.
  - 7.3. Trental (Pentoxyfilline):
    - 7.3.1. Several mechanisms of action have been proposed for the potential benefits of Trental in radiation induced injury. However, the exact mechanism is unclear. Trental may decrease the inflammatory response and formation of oxygen radicals (2,9). The dosage of Trental used in this study is typically well tolerated and presents minimal risk to the patient. Common side effects of Trental include gastrointestinal effects such as nausea, vomiting, dyspepsia; nervous system effects such as headache, dizziness, insomnia and cardiovascular effects such as palpitations, flushing and angina. While typically minor, side effects have necessitated discontinuation of Trental in approximately 3% of treated patients.
  - 7.4. The benefits of this study include the possibility of providing a prophylactic regimen for the prevention of radiation necrosis.
- 8. Payment

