## **TO DETECT RN REDUCTION FROM 15% (HISTORICAL) to 10%** (a 33.3% reduction)

#### Possible Designs For P0=0.850, P1=0.900, Alpha=0.050, Beta=0.200

								Constraints
N1	R1	PET	Ν	R	Ave N	Alpha	Beta	Satisfied
124	106	0.598	288	254	189.88	0.047	0.198	Optimum

In the first stage, we need to see 124 lesions on supplement and if we find 106 or less lesions RN-free, the trial stops. If you find 107 or more lesions RN free, the trial continues and we go all the way to 288 lesions. If we find 255 or more lesions RN free (in other words- 33 or fewer RN), we have proven that the trial succeeded in reducing the RN incidence from 15% to 10% by giving them supplement.

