# **TO DETECT RN REDUCTION FROM 15% (HISTORICAL) to 7.5%** (a 50 % reduction)

#### Possible Designs For P0=0.850, P1=0.925, Alpha=0.050, Beta=0.200

N1	R1	РЕТ	Ν	R	Ave N	Alpha	Beta	Constraints Satisfied
52	44	0.528	134	120	90.69	0.047	0.2000pti	mum & Minimax

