#### **Report Definitions**

N1 is the sample size in the first stage.
R1 is the drug rejection number in the first stage.
PET is the probability of early termination of the study.
N is the combined sample size of both stages.
R is the combined drug rejection number after both stages.
Ave N is the average sample size if this design is repeated many times.
Alpha is the probability of rejecting that P<=P0 when this is true.

Beta is the probability of rejecting that P>=P1 when this is true.
P0 is the response proportion of a poor drug.
P1 is the response proportion of a good drug.

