#### **Summary Statements**

The optimal two-stage design to test the null hypothesis that  $P \le 0.850$  versus the alternative

that P>=0.950 has an expected sample size of 33.71 and a probability of early termination of

0.602. If the drug is actually not effective, there is a 0.049 probability of concluding that it is (the target for this value was 0.050). If the drug is actually effective, there is a 0.200 probability of concluding that it is not (the target for this value was 0.200). After testing the drug on 13 lesions in the first stage, the trial will be terminated if 11 or fewer respond. If the trial goes on to the second stage, a total of 65 lesions will be studied. If the total number responding is less than or equal to 59, the drug is rejected.

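### Section 4.4.3 does not reproduce the Appendix A stage-1 rule it cites: the two disagree when the 8th necrosis arrives at exactly 52 lesions, and 4.4.3 does not require the 52 to have been assessed.

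*Combined protocol and SAP*

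**What the plan says.** Section 4.4.3 presents its interim look as following the design in Appendix A. The look is triggered by the 8th lesion with necrosis, and the decision then depends on how many lesions have been entered: "If at that stage, we have 52 or more lesions in the study then that would confirm we should continue" to the full 134. It sets no follow-up or assessment condition for those lesions, does not say whether accrual pauses, and leaves the stop action to be inferred.

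Appendix A gives the design under "Possible Designs For P0=0.850, P1=0.925, Alpha=0.050, Beta=0.200": N1 = 52, R1 = 44, PET 0.528, N = 134, R = 120, average N 90.69, alpha 0.047. The Report Definitions say that "R1 is the drug rejection number in the first stage". The other two designs in the appendix show how such a rule is meant to work. For 15% to 10%, 124 lesions are observed and "if we find 106 or less lesions RN-free, the trial stops". For 15% to 5%, "After testing the drug on 13 lesions in the first stage, the trial will be terminated if 11 or fewer respond".

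Three other passages bear on when RN can be known:

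- Section 4.4.6.2 lists four alternative criteria for RN, one of which is "2 consecutive scans with persistent MRI changes consistent with radiation necrosis".
- Section 4.4.4 has the follow-up and MRI forms completed "Every 3 months for 1 year".
- Section 5.1 expects that "the patient recruitment period will be 2 years and the follow up period will be one year", three years in all.

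**The concern.** Appendix A fixes the number of lesions and counts outcomes. Section 4.4.3 fixes the number of outcomes and counts lesions. The two are equivalent only if the boundary is set correctly and every counted lesion has a known outcome.

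Neither condition is secured. At the boundary, identical data lead to opposite decisions. Beyond it, a lesion entered shortly before the 8th RN counts towards the 52 although nothing is yet known about it. Detection delay can only increase the number of lesions entered by the time of the 8th RN, so it can only make continuation more likely.

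This is the plan's only futility stop. At stake are the probability of stopping an ineffective regimen early and the expected trial size that Appendix A reports.

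**Working it through.** **Inputs.** From Appendix A: null RN rate 15% (P0 = 0.85), N1 = 52, R1 = 44, N = 134, R = 120. From 5.1: accrual over 24 months. Lesions are treated as independent, as in 6.4. Times from entry to detected RN, even entry and slower accrual are assumptions.

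**1. The plan's own figures reproduce.** 44 or fewer RN-free of 52 means 8 or more RN.

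- PET = P(Bin(52, 0.15) ≥ 8) = 0.528.
- Average N = 52 + 82 × (1 − 0.528) = 90.69, using the unrounded PET.
- R = 120 requires 121 or more RN-free for success, that is 13 or fewer RN. Type I error is then 0.0471.

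**2. The boundary, with every outcome known at once.** Under 4.4.3 the trial stops only if the 8th RN occurs by lesion 51: P(Bin(51, 0.15) ≥ 8) = 0.505. The difference, 0.528 − 0.505 = 0.023, is the probability that the 8th RN falls exactly on lesion 52.

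**3. The literal count, with a fixed delay d.** With even entry the spacing is s = (accrual months)/134. When RN in lesion i is detected, i + floor(d/s) lesions have been entered. The trial stops only if the 8th RN is among the first k = 51 − floor(d/s) lesions, with probability P(Bin(k, 0.15) ≥ 8).

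| Accrual | Delay | k | Chance of stopping |
|---|---|---|---|
| 24 months | 1 month | 46 | 0.385 |
| 24 months | 3 months | 35 | 0.144 |
| 24 months | 6 months | 18 | 0.003 |
| 36 months | 3 months | 40 | 0.244 |
| 36 months | 6 months | 29 | 0.059 |
| 48 months | 3 months | 43 | 0.313 |
| 48 months | 6 months | 35 | 0.144 |

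**4. Spread delays, by simulation with even entry.** At 24 months, detection uniform over 0–3 months gives about 0.31, uniform over 0–6 months about 0.14, and uniform over 3–12 months below 0.001. At 48 months, uniform over 0–3 months gives about 0.41 to 0.42.

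**5. Average size at 15% RN on the literal count, 24 months.** About 121 lesions if RN is seen at 3 months and about 134 if at 6 months, against 90.69.

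**6. Type I error.** With no stop at all, P(Bin(134, 0.15) ≤ 13) = 0.0494, against 0.0471 with the Appendix A stop.

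**The case against.** The strongest defence is that 4.4.3 is loose shorthand. It points to Appendix A at both ends and uses that design's numbers: 8 is 52 − 44, and 134 is the full size. A statistician who followed the cross-reference would apply 44 of 52. On that view lesions in the study means lesions with known outcomes, and the whole discrepancy is the tie at 52, worth 0.023. This stands in part. The documents do not say that unassessed lesions are to be counted; they only fail to exclude them. But the tie is wrong on either reading, and 4.4.3 is the passage that states how the interim look will be run.

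A reader might go further and infer that the futility stop would hardly ever act. The documents do not support that across the plausible range. The four RN criteria are alternatives, and only the two-scan criterion cannot be met on scheduled scans before month 6. Steroid requirement, spectroscopy or histology could identify RN earlier, and with detection spread over 0–3 months the chance of stopping is still about 0.31 at 24-month accrual. The documents give no onset distribution from which to choose between such cases.

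A reader might also infer that false-positive risk is inflated. It is not: losing the stop moves type I error only from 0.047 to 0.049 at 13 or fewer RN. How many RN the final success rule in 4.4.3 allows is a separate matter.

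It is also fair to say that the cost is bounded: at most about 43 extra lesions on average (134 − 90.69), or about 16 patients at 2.75 lesions each, on a regimen that section 7 describes as minimal risk.

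**Conclusion.** The point holds. What is certain from the text is that 4.4.3 and Appendix A give opposite decisions when the 8th RN arrives at 52 lesions, so that 4.4.3 delivers an early-stopping probability of 0.505 at best instead of 0.528, and that 4.4.3 sets no assessment condition for the lesions it counts.

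On the literal wording, any detection delay lowers the probability further. That direction needs no assumption about onset or accrual; the size does. At 15% RN with even entry over 24 months, it runs from about 0.39 (1-month delay) to 0.003 (6 months). Slower accrual softens the loss without restoring 0.528. The stated average of 90.69 lesions is lost with it. The harm is confined to early stopping and expected size; the final test's error rate is essentially unaffected. All figures assume independent lesions. Since this is the only futility rule, the two sections need to be reconciled before it is applied.

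**What to change.** Replace the stage-1 sentences of 4.4.3 with a rule that matches Appendix A, for example:

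> Stage 1 is the first 52 lesions in order of entry. Where a patient enters several lesions, their order is fixed at enrolment, before any outcome is known. The trial stops as soon as 8 of these 52 have RN. It continues if 7 or fewer have RN once each of the 52 has RN, has completed the scheduled 12-month MRI follow-up, or has died or left.

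The within-patient order is needed because lesion 52 may fall inside a patient with several lesions. The section should also say how lesions without complete follow-up are counted and that their number will be reported, say whether accrual pauses, and restate PET and average sample size for the options chosen.

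**Cost.** The core is wording and lesion-level bookkeeping from scans already scheduled. If no RN goes unseen, the rule stops with probability 0.528 at 15% RN and 0.039 at 7.5%. Three consequences should be stated openly:

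- **Unseen RN.** If a fraction f of RN among the 52 is never observed and those lesions count as RN-free, PET is P(Bin(52, 0.15(1 − f)) ≥ 8) = 0.40, 0.28 or 0.17 for f = 10, 20 or 30% (assumed). Even with a pause, the mean 52 + 82 × (1 − PET) is then about 101, 111 or 120 lesions.
- **With a pause.** Lesion 52 enters at 52 × 24/134 = 9.3 months and completes follow-up at 21.3. The other 82 take 82 × 24/134 = 14.7 months, so accrual ends at about month 36 and follow-up at about month 48, against the 3 years in 5.1.
- **Without a pause.** Mean enrolment at 15% RN and 24-month accrual rises above 90.69: about 93, 102 or 109 lesions if RN is seen at 3 months, at 6 months, or over 3–12 months (assumed).

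### Section 4.4.3 counts RN over a fixed 134 lesions with no rule for lesions lost before RN can be seen, so they score as RN-free; the net bias depends on how the 15% benchmark was counted.

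*Combined protocol and SAP*

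**What the plan says.** The final rule in section 4.4.3 is a count. If the first stage is passed, the trial is to "continue to complete the study with all 134 lesions"; then, "if we find 14 or less lesions with radiation necrosis, we would then claim that the study has met its objective". The first-stage look is also a count, taken at the eighth RN lesion: "If at that stage, we have 52 or more lesions in the study", the trial goes on.

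Appendix A gives the design row "52 44 0.528 134 120 90.69 0.047" (n1, r1, PET, N, R, average N, alpha). It codes non-RN as success. In its worked example for the 288-lesion design it turns RN-free lesions into RN lesions by subtraction from N. There are two categories only, RN and RN-free.

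On follow-up, section 4.3.2 schedules MRI every 3 months and section 4.4.4 asks for forms every 3 months for a year. Section 5.1 states that "the follow up period will be one year", while section 4.3.3 says "All patients will be followed for an appropriate duration as clinically indicated". Section 4.4.6.2 lists four alternative routes to an RN diagnosis: radiographic change with a steroid requirement, "2 consecutive scans with persistent MRI changes consistent with radiation necrosis", MR spectroscopy, or histology.

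Section 6.4 derives 49 patients from 134 lesions at 2.75 lesions each, with no allowance for loss. No section defines an evaluable lesion, a minimum follow-up, replacement, censoring, or the handling of death.

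**The concern.** RN can be recorded only if someone looks: by scan, spectroscopy or tissue. A lesion never imaged after radiosurgery will almost never enter the RN count, but it stays among the 134. Under a two-category rule it then adds to the RN-free side. The patients have brain metastases, so some deaths and losses within a year must be expected.

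The trial has one arm, so no concurrent control loses lesions in the same way. The only comparator is a fixed 15%. If that figure came from better-ascertained lesions than this trial will have, an inactive regimen can look protective because of missing follow-up alone. The first-stage look has the same weakness: lesions enrolled shortly before the eighth RN count towards the 52 although RN has had little time to appear in them.

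**Working it through.** **Inputs.** From Appendix A, "Possible Designs For P0=0.850, P1=0.925, Alpha=0.050, Beta=0.200", with n1 = 52, r1 = 44, N = 134, R = 120. Success therefore needs at least 121 RN-free lesions, that is RN ≤ 134 − 121 = 13. From section 6.4, 49 × 2.75 = 134.75 lesions, so the number enrolled equals the number analysed. The unassessable share u is not in the documents; it is an assumption, shown over a range.

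**Formula.** For RN-free probability q,

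P(success) = Σ over x = 45 to 52 of b(x; 52, q) × P[Bin(82, q) ≥ 121 − x].

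**Reproducing the plan.** At q = 0.85: PET = P[Bin(52, 0.85) ≤ 44] = 0.528; average N = 52 + (1 − 0.528) × 82 = 90.69 (unrounded PET); alpha = 0.0471. All three match Appendix A. At q = 0.925 the power is 0.856, so beta is 0.144 and not the printed 0.200; that is a separate matter.

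**Effect of loss, if the 15% is fully ascertained.** With a share u scored RN-free by default, q = 1 − 0.15 × (1 − u).

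| u | Apparent RN rate | P(false success), RN ≤ 13 |
|---|---|---|
| 0 | 15.0% | 0.047 |
| 5% | 14.25% | 0.075 |
| 10% | 13.5% | 0.115 |
| 20% | 12.0% | 0.243 |
| 30% | 10.5% | 0.437 |

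At u = 50% the apparent rate is 0.15 × 0.5 = 7.5%, exactly the target. A simulation that loses whole patients (49 patients with 2 or 3 lesions each) gives 0.119, 0.254 and 0.437 at 10%, 20% and 30%, so losing lesions in clusters hardly changes the result.

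Section 4.4.3 prints a cut-off of 14, not 13. That alone gives 0.077 with no loss at all. It is a separate error and is kept out of the table.

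**If the benchmark carries the same loss.** Suppose the 15% is a crude rate over all treated lesions, a share f of which was never assessed. A trial with the same loss and no drug effect then also shows a crude 15%, and the false-success probability stays near 0.047. The rate among assessed lesions is 0.15/(1 − f): 16.7% at f = 10% and 18.75% at f = 20%.

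**Cut-offs for an evaluable-lesion test.** The largest RN count with two-stage alpha ≤ 0.05 at an RN rate of 15% (n1 = 52, r1 = 44), and the power:

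| Evaluable lesions | Cut-off | Alpha | Power at 7.5% RN |
|---|---|---|---|
| 134 | 13 | 0.047 | 0.86 |
| 121 | 11 | 0.038 | 0.80 |
| 107 | 9 | 0.031 | 0.72 |

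If the 15% is instead crude, a true halving among assessed lesions is 0.075/(1 − f), or 8.3% and 9.4%. The same cut-offs then have power 0.68 at 121 lesions (f = 10%) and 0.45 at 107 (f = 20%).

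**The case against.** The strongest objection concerns the benchmark. Section 6.4 says the trial treats lesions as the institution's published series did, section 4.4.6.2 takes its RN definition, and section 2.2.1.1 quotes 14% of treated lesions. If that series also kept unassessed lesions in its denominator, the dilution is on both sides and may cancel. An evaluable-only test against a crude 15% would then be unfair to the regimen, as the power figures of 0.68 and 0.45 show. This stands: the documents do not say how the series handled death and loss, so the size of the net bias is not established.

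Two further limits also stand. The plan never says in words that a lost lesion is RN-free; that follows from the fixed count, the two-category coding and the absence of any other rule. And a reader might infer that a lesion with a single scan cannot be classed as RN. The documents do not support that: the four criteria are alternatives, and three of them do not ask for two consecutive scans. A two-scan threshold for evaluability would thus be arbitrary. If it applied only to RN-free lesions, entry to the denominator would depend on outcome.

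The entry safeguards (availability for follow-up in 6.5.3, exclusion of interfering illness in 6.6.4) and the 3-monthly MRI schedule should limit avoidable loss. They do not say how a lesion is counted after death or dropout, so they do not answer the point.

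**Conclusion.** The gap is real. Applied as written, section 4.4.3 scores a lesion that could not be assessed as a success, and this lowers the observed RN rate whatever the drug does. If the 15% is a fully ascertained rate and 10%, 20% or 30% of lesions are unassessable, the false-success probability rises from 0.047 to 0.115, 0.243 or 0.437 with the Appendix A cut-off. Both conditions are assumptions.

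A reader might go further and infer that the comparison with history is certainly biased towards success by these amounts. The documents do not support that, because similar loss behind the benchmark would remove part or all of the effect. What is established is that the claim of a 50% reduction rests on a count whose meaning depends on two things the plan leaves open: how many lesions can be assessed, and what kind of rate the 15% is.

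**What to change.** In section 4.4.3:

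1. Keep the all-lesion count for comparison with the historical rate, but do not claim the 50% reduction on it alone.
2. Add a 12-month per-lesion cumulative incidence of RN, with death as a competing event and lesions otherwise censored at last MRI. Its confidence interval should allow for several lesions per patient. It uses MRI data already scheduled.
3. Report the number of lesions with no post-radiosurgery MRI. Repeat the test without them as a sensitivity analysis, counting RN by any of the four criteria. Use the largest cut-off that keeps two-stage alpha at or below 0.05 for the actual number of evaluable lesions (for example 13 for 134, 11 for 121, 9 for 107).
4. State whether the 15% is a crude or an evaluable-lesion rate, and compare like with like.

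The cost is some wording, a little more analysis, and lower stated power in the sensitivity test: 0.80 at 121 and 0.72 at 107 lesions if the evaluable null is 15%, and less if the benchmark is crude.

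### Section 4.4.3 declares success at 14 necrotic lesions of 134, a count the adopted Simon design rejects, and calls the result a 50% reduction

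*Combined protocol and SAP*

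**What the plan says.** Section 4.4.3 sets the only efficacy decision rule. If the first stage is passed, "we should continue to complete the study with all 134 lesions"; then "if we find 14 or less lesions with radiation necrosis, we would then claim that the study has met its objective", which it describes as a "50% reduction in incidence of radiation necrosis (from 15% to 7.5%). (see Appendix A"). Section 6.4 gives the same total: "a total of 134 lesions are necessary to show a 50% effective reduction in radiation necrosis with our supplement".

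Appendix A, in which an RN-free lesion is a success, lists the matching design under "Possible Designs For P0=0.850, P1=0.925, Alpha=0.050, Beta=0.200": N1 = 52, R1 = 44, PET 0.528, N = 134, R = 120, average N 90.69, alpha 0.047, beta 0.200. Its Report Definitions state that "R is the combined drug rejection number after both stages". It applies that meaning in words to the other two designs:

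- 15% to 10%, with R = 254 of 288: "If we find 255 or more lesions RN free (in other words- 33 or fewer RN") the trial has succeeded.
- 15% to 5%, with R = 59 of 65: "If the total number responding is less than or equal to 59, the drug is rejected".

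The 15% to 7.5% design, the one adopted, has no worked sentence of its own in Appendix A.

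**The concern.** Two things in the same sentence of 4.4.3 look wrong.

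1. **The cut-off.** The number 14 is 134 − 120, the necrosis count at the rejection value. The first count that succeeds is one lesion lower. The body of the protocol therefore accepts a result that its own design rejects, and the type I error is no longer the tabulated one.
2. **The claim.** Crossing the final boundary of a Simon design rejects the null rate of 15%. It does not show that the rate is 7.5%. As worded, any count up to the cut-off can be reported as a halving of necrosis, including counts where the observed reduction is about a third.

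The trial is single-arm, so there is no concurrent control to temper an overstated conclusion.

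**Working it through.** **Inputs.** From Appendix A: n1 = 52, r1 = 44, n = 134, R = 120, success = RN-free, p0 = 0.85, p1 = 0.925, target alpha 0.05 and beta 0.20. From 4.4.3: final rule of 14 or fewer RN. Lesions are treated as independent, as in section 6.4.

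**Step 1: what R means.** R or fewer successes rejects the treatment, so success needs R + 1.

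| Design | R | Successes needed | Largest RN count that succeeds |
|---|---|---|---|
| 15% to 10% | 254 of 288 | 255 | 288 − 255 = 33 (Appendix A says 33) |
| 15% to 7.5% | 120 of 134 | 121 | 134 − 121 = 13 (4.4.3 says 14) |

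**Step 2: reproduce the tabulated design.** Let q be the RN rate. The first stage continues with 7 or fewer RN in 52.

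- PET = P(8 or more RN in 52 at q = 0.15) = 0.5281 (table: 0.528).
- Average N = 52 + (1 − 0.5281) × 82 = 90.69 (table: 90.69).
- P(claim) = Σ over x = 0 to 7 of Bin(x; 52, q) × P(Bin(82, q) ≤ c − x), where c is the final RN cut-off.
- At q = 0.15 and c = 13: alpha = 0.0471 (table: 0.047).

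The tabulated alpha therefore belongs to 13 or fewer. The tabulated beta does not reproduce: at q = 0.075 and c = 13 the exact beta is 0.144. A beta of 0.200 arises at q = 0.08. This discrepancy affects neither alpha nor the choice between 13 and 14.

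**Step 3: the rule as written.** Section 4.4.3 and Appendix A do not describe the first stage identically, so several readings were computed.

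| First stage | Alpha, 13 or fewer | Alpha, 14 or fewer |
|---|---|---|
| Appendix A: continue with 7 or fewer RN in 52 | 0.0471 | 0.0770 |
| 4.4.3 read literally: 8th RN occurs at lesion 52 or later | 0.0474 | 0.0776 |
| Continue with 8 or fewer RN in 52 | 0.0488 | 0.0813 |
| No interim stop | 0.0494 | 0.0832 |

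Under every reading 13 keeps alpha below 0.05 and 14 does not. With the Appendix A first stage:

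| True RN rate | P(claim), 13 or fewer | P(claim), 14 or fewer |
|---|---|---|
| 15% (null) | 0.047 | 0.077 |
| 10% (a 33% reduction) | 0.51 | 0.61 |
| 7.5% (design alternative) | 0.856 | 0.903 |

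**Step 4: what the boundary counts show.** Bounds are exact Clopper-Pearson limits for a fixed sample of 134; they ignore the two stages. The reduction is 1 − rate/0.15.

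| RN count | Rate | Observed reduction | One-sided 95% upper bound |
|---|---|---|---|
| 14 | 10.4% | 30% | 15.85% |
| 13 | 9.7% | 35% | 14.98% |
| 10 | 7.5% | 50% | 12.3% |

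The one-sided bound excludes 15% at 13 and not at 14. A 7.5% rate corresponds to 0.075 × 134 = 10.05 lesions, so counts of 11 to 14 would be reported as a 50% reduction although the point estimate falls short of it.

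**The case against.** The strongest reply is that little turns on this. The two cut-offs differ at one outcome, exactly 14 of 134, and the extra false-positive probability is 0.0770 − 0.0471 = 0.030 in a phase II trial. The 50% wording can be read as naming the design by its target effect, as Appendix A does for the 15% to 10% design. It is also a separate fault, since changing 14 to 13 does not cure it.

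The narrow scope is real, but a threshold that breaches the plan's own alpha limit is still an error. The claim is indeed a separate fault and needs its own correction. Section 4.4.3 goes beyond naming a target: it says what will be claimed.

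Three further points stand as refinements:

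- The two-sided 95% interval does not separate the rules. It is 5.8% to 16.9% at 14 and 5.3% to 16.0% at 13, so both include 15%. Only the one-sided bound matches the one-sided test, and the report should name it.
- The power of 0.856 disagrees with the tabulated beta of 0.200, and that should be acknowledged.
- About 49 patients contribute the 134 lesions. Within-patient correlation would probably raise the true type I error under either cut-off; the documents give no intraclass correlation with which to size it.

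**Conclusion.** The rule is wrong as written. Under Appendix A's definition of R, and its worked use of R in both other designs, 14 necrotic lesions is a rejection, while 4.4.3 makes it a success. The error raises the type I error from 0.047 to 0.077 with the Appendix A first stage (0.0770/0.0471 = 1.63 times), and to as much as 0.083 with no interim stop.

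Separately, the 50% claim does not follow from passing the test at either cut-off. If the true rate is 10%, that claim would be made with probability 0.61 under the written rule and still 0.51 under the corrected one.

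The figures assume independent lesions and take the 15% historical rate as given; they do not depend on whether 15% is the right benchmark.

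**What to change.** In 4.4.3, if the 15% null is kept:

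1. Set the success criterion to 13 or fewer necrotic lesions, stated also as 121 or more of 134 RN-free so that it can be checked against R = 120.
2. Replace the claim of a 50% reduction with the conclusion that necrosis incidence is below 15%, reported with the point estimate and a one-sided 95% upper bound (equivalently, the upper limit of a two-sided 90% interval).
3. Mention a 50% reduction only as a point estimate, and only if 10 or fewer of 134 lesions are necrotic. This is a suggested reporting convention and not part of the Simon design.

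Also add the missing worked sentence for this design to Appendix A, recheck the tabulated beta, and state that the operating characteristics assume independent lesions.

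The cost is a few wording changes. Power at a 7.5% rate goes from 0.903 to 0.856, above the planned 0.80. No lesions, patients or visits are added.
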